Achieving adequate pain control in trauma patients proves challenging. Consequences of uncontrolled pain include immobility, respiratory compromise, exhaustion due to lack of sleep, disorientation, agitation, stress response, and post-traumatic stress disorder. The standard of care for analgesia in poly-trauma patients is the use of opioids administered via intravenous, epidural, or enteral routes with either intermittent dosing or as patient-controlled analgesia. Though opioid agents can provide effective analgesia, they exhibit untoward effects that at times may be dose limiting. These adverse effects include hypotension, bradycardia, central nervous system depression, respiratory depression, somnolence, and nausea. Additional common side effects of opioid use include pruritus, dry mouth, urinary retention, vomiting, prolonged recovery of ileus, and constipation. Clinicians are becoming increasingly aware of additional consequences, such as, opioid tolerance necessitating increased doses, opioid induced hyperalgesia, and opioid dependence. As such, increasing emphasis has been placed on a multimodal approach to the management of postoperative and post-traumatic pain. This multimodal approach includes use of local and regional blocks using local anesthetics.

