- 14) Pediatric patients <18 years old
- 15) Patients exhibiting signs of shock upon admission, HR >120 or SBP <100 mmHg.
- 16) History of allergic reaction to local anesthetics
- 17) Administration of any other local anesthetic in the 2 hours prior to the study enrollment.
- 18) Distal femur fractures

7) Number of Subjects

17 patients per arm

Total subjects: 34

8) Recruitment Methods

Subjects will be recruited from the UC Davis Trauma Center. Patients found to have femur and /or hip fractures admitted to UCDMC will be screened for eligibility.

Waiver of HIPAA authorization for recruitment is requested for access to PHI during the screening to determine eligibility.

Description of PHI that will be accessed.

Information reviewed to assess eligibility will include: date of admission, date of birth, gender, mechanism of trauma injury (blunt/penetrating), x-rays, lab results, admission vital signs, home medications and the patient's medical history.

The use of PHI involves no more than minimal risk and granting of waiver will not adversely affect privacy of the patients.

Access to medical records that contain patient's personal information for the purpose of this study will be limited to the approved research personnel. These personnel already have knowledge of and access to identifiable medical information of current trauma patients as part of their daily job functions; hence, granting of this waiver will not adversely affect the privacy of the involved patients or the confidentiality of their information. EMR access to PHI is password-protected and no PHI will be reused or disclosed to any

other person or entity, except as required by law. Data will be used solely for the purposes of determining study eligibility.

The research could not practicably be conducted without a waiver or alteration.

Without an initial review of the medical record for screening purposes, it would not be possible to identify potential subjects and confirm their applicability for study participation.

The research could not practicably be conducted without access to and use of PHI.

Since PHI is embedded in the medical record and since the screening process requires detailed information about trauma patients, access to medical records (viewing of PHI) is necessary.

9) Compensation to the Subjects

Subjects will not be compensated for this study.

10) Study Timelines

The duration of each subject's participation is the length of their hospital stay.

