Duration anticipated to enroll all study subjects: 12 months.

Data acquisition and analysis: same 12 months

Manuscript preparation: 6 months

Total time requirement: 1.5 years

11) Study Endpoints

Hypothesis: In patients with femur or hip fractures, a fascia iliaca compartment block using liposomal bupivacaine will require less total opioid administration compared to a fascia iliaca block using 0.2% ropivacaine.

Primary Endpoint

(1) Total opioid requirement during the 96 hour randomization period measured in milligram morphine equivalents.

Secondary Endpoint

(1) Percentage of time during the 96 hour randomization period that the objective pain score was above mild (defined as a numeric rating score >4).

12) Procedures Involved

The nature of the risks and benefits associated with participation in the study will be explained to all potential study subjects. Written informed consent must be obtained before the subject can begin any screening procedures that are not considered standard patient care. Subjects who have undergone the screening procedures and have met the entry criteria will be randomized into the study and assigned to treatment by the Unblinded Pharmacist. Subjects will be randomized in a computer-generated, blinded block, 1:1 ratio to treatment with 60mL of either 0.2% ropivacaine (120mg) or a dilution of liposomal bupivacaine (266mg).

The Pharmacy and Emergency Medicine (EM) members will be the only unblinded study team members. All other members, including the Trauma team and Clinical Research Coordinator (CRC), will remain blinded.

The unblinded Investigational Drug Service (IDS) Pharmacy at UC Davis Health (UCDH) will be responsible for blinding and drug preparation. Investigational Product (IP) will be prepared in three 35mL Luer lok syringes, each containing 20mL of IP, for a total dose of 60mL. In addition to a patient-specific institutional label, masking/amber tape will also be affixed to the syringes in order to reduce the risk of drug recognition by a supporting procedure nurse. During the procedure, nursing care of the patient will temporarily transition from the primary bedside nurse to a supporting procedure nurse. The supporting procedure nurse will remain blinded and will assist primarily with assessments and recording of vital signs (but will not work directly with the IP).

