The patient will be blinded and all members of the healthcare team will be blinded from the point of transfer of care from the Emergency Department physicians to the receiving service.

Both groups will be able to receive as needed analgesia per the primary attending service. (e.g., oral hydrocodone/acetaminophen 5/325 mg or narcotic IV push as needed for breakthrough pain).

Patients enrolled in the study will be given a light blue wristband for identification to alert physicians regarding restrictions for anesthetics. Additionally, an automatic alert notification will be given by the Electronic

Medical Record system if additional local anesthetics are ordered for the patient.

Pain Assessment

Objective pain assessment will be evaluated by the UCDMC nursing staff per local standard of care which is every four hours while the patient is awake using a numeric rating scale (NRS) of 0 to 10 with a pain score of 0 being defined as: no pain, 1-4 mild pain, 5-7 defined as moderate pain, and 8-10 defined as severe pain.

Study Definitions

Acute and hospital-related adverse effects and study outcomes will be collected and tracked prospectively during the FICB and throughout the hospital stay, as appropriate per endpoint.

During hospital stay study outcomes

Data collection will include total amount of opioids administered to study patients in morphine equivalents (see Appendix) and the use of other analgesic medications during this time period. Adjunctive analgesic use including non-steroidal anti-inflammatory drugs, acetaminophen, and gabapentin will be quantified. Use of additional adjunctive agents such as muscle relaxants also will be collected.

All objective pain and agitation scores reported by the NRS will be collected; duration of supplemental oxygen requirement; number of episodes of oxygen desaturation (arterial O₂ sat below 92%); morning incentive spirometer and peak flow measurements; 24-hour antiemetic (e.g., promethazine; ondansetron) pharmacotherapy; time to first bowel movement; and need for anti-hallucination or anti-delirium pharmacotherapy.

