Additional outcomes: hospital lengths of stay; time from study drug initiation to maximum allowable ambulation per injury pattern; post-discharge opioid type and dosage provided at the time hospital discharge prescription; and patient report of chronic pain syndromes. Adverse effects including the incidence of hypertension requiring antihypertensive pharmacotherapy in addition to the patients home regimen, hypotension (SBP < 90 mmHg) requiring fluid bolus/vasoactive pharmacotherapy, tachycardia requiring pharmacologic intervention (defined as HR greater than 100 bpm), bradycardia (defined as HR below 60 beats per minute with symptoms or hypotension), respiratory depression (apnea; transition to higher level of respiratory support), emesis, hallucinatory reactions or experiences per patient interview, and pruritus per physical exam.

The study will be stopped if ≥2 patients receiving the active study drug develop the same Grade 3 adverse reaction (Adverse Event Severity

Definition defined previously) or if one patient develops a Grade 4 or higher adverse reaction.

13) Data and Specimen Banking

Not applicable.

14) Data Management and Confidentiality

Each patient will be assigned a unique study ID number at the time of study entry. Study information stored by the research personnel at UCDMC, which may include name and medical record number, will be kept strictly confidential and available only to the principal investigator and trained staff assigned to this study. All information will be kept secure in locked file cabinets accessible only by research personnel. All identifiers for recruitment purposes will be destroyed within 2 years of completion of study.

Statistical Analysis

Data will be presented as means \pm standard errors of the mean (primary endpoint) and proportions \pm interquartile ranges (secondary endpoint). Following assessment for normality, primary endpoint data will either be subjected to parametric unpaired two-sided t-tests or nonparametric Wilcoxon rank sum test Mann-Whitney two sample statistic. Significance will be set at $p = 0.05$. Secondary endpoint proportions will be assessed using either nonparametric chi-square tests or Fisher's exact test.

Other data such as ICU and hospital lengths of stay and adverse events will be collected, summarized, and described. Exploratory analyses these data may be attempted, but these will be hypothesis generating, given the small sample size used in this pilot study.

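### The primary 96-hour opioid total includes any continued pre-injury opioid regimen, and nothing in the plan accounts for it; the cost is precision, not bias

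*Combined protocol and SAP*

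**What the plan says.** Section 11 (Study Endpoints) defines the primary endpoint as "Total opioid requirement during the 96 hour randomization period measured in milligram morphine equivalents". Section 12 (Procedures Involved, hospital-stay outcomes) collects it as the "total amount of opioids administered to study patients in morphine equivalents". Neither place mentions opioids taken before the injury, so counting them is the literal meaning of a total and not an explicit rule.

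No other part of the plan deals with them:

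- **Eligibility (section 6).** None of the 18 exclusions concerns long-term opioid or opioid-agonist use. The medication-based ones cover certain anticoagulants and "Administration of any other local anesthetic in the 2 hours prior to the study enrollment".
- **Allocation (sections 12 and 30).** Randomization is 1:1 in blocks, with no stratification factor stated.
- **Analysis (Statistical Analysis, under section 14).** An unadjusted two-sided t-test or Wilcoxon rank sum test is chosen after a normality assessment. The primary endpoint is presented as mean and SEM.
- **Sample size (section 7).** "17 patients per arm".

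The needed information is already in hand: section 8 lists "home medications and the patient's medical history" among the items reviewed at screening. Section 12 also defines one adverse event net of usual treatment, namely "hypertension requiring antihypertensive pharmacotherapy in addition to the patients home regimen".

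**The concern.** The trial asks whether a longer-acting block reduces the opioid needed for acute fracture pain. A scheduled home opioid carried on for four days is largely not a response to that pain, yet each dose enters the primary total. A patient taking H morphine mg equivalents per day at home contributes 4H before any acute need is counted.

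Two things are at stake. The first is power in a trial of 34 patients. The second is what the pilot hands on: section 4 says its long-term goal is to inform larger multicenter trials, and those would be planned from a mean and spread that a few maintenance patients can shift considerably.

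**Working it through.** **1. The plan's own figure.** Section 7 gives 17 per arm. The text available gives no effect size, SD or power, so the figure cannot be reproduced. Inverting the two-sample t-test at two-sided 0.05 with 17 per arm gives a detectable standardized difference of 0.99 at 80% power.

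**2. Assumptions (none from the documents).** Lognormal 96-hour totals with CV 0.6; true ratio 0.55 (a 45% reduction); k of 34 patients, allocated at random, each with a fixed home dose of m times the comparator mean total. The normality check is taken as Shapiro-Wilk in each arm, because the plan names no test.

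**3. Shift in an arm mean.** If all k patients fall in one arm, its mean moves by k × m / 17 of the comparator mean:

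- k = 2: 2/17 = 0.12 (m = 1); 4/17 = 0.24 (m = 2)
- k = 3: 3/17 = 0.18 (m = 1); 6/17 = 0.35 (m = 2)

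The assumed true difference is 0.45. The chance that all fall in the same arm is 2 × (17/34)(16/33) = 0.48 for two patients and 2 × (17/34)(16/33)(15/32) = 0.23 for three. Either arm is equally likely, so this is noise in both directions.

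**4. Inflation of the SD.** With prevalence p, the comparator variance in units of mean squared is CV² + p(1 − p)m². For p = 0.06:

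- m = 2: √(0.36 + 0.06 × 0.94 × 4) / 0.6 = 1.28; a sample size planned from it grows by 0.5856 / 0.36 = 1.63
- m = 1: √(0.36 + 0.0564) / 0.6 = 1.08; sample size × 1.16
- m = 0.5: √(0.36 + 0.0141) / 0.6 = 1.02; sample size × 1.04

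**5. Simulated power.** Repeat runs differ by up to about two points.

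| Home-opioid patients | Home dose | t-test | Wilcoxon | Planned gated choice |
|---|---|---|---|---|
| none | – | 81% | 84% | about 86% |
| 2 | 1 × mean | 69% | 76% | 76% |
| 2 | 2 × mean | 47% | 73% | 74% |
| 3 | 1 × mean | 64% | 72% | 73% |
| 3 | 2 × mean | 38% | 68% | 69% |

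With two patients at 0.25 to 0.5 times the mean, the gated choice keeps 82-84%.

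**6. A second set of assumptions.** Normal totals truncated at zero, comparator mean 100 or 200 MME, SD half the mean, true standardized difference 0.99, home dose 30 to 120 MME/day in 2 to 3 patients. Over 96 hours that adds 120 to 480 MME, or 1.2 to 4.8 times a mean of 100 and 0.6 to 2.4 times a mean of 200. Power of the gated choice falls from about 80% to 60-69% (mean 100) or 58-77% (mean 200). The t-test alone falls to 13-66% or 33-77%. Type I error stays at 0.025-0.052. In the most extreme case (mean 100, 120 MME/day) the observed mean difference has the wrong sign in 17-18% of trials, against 0.2% with the home opioid removed.

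**7. What restores the loss.** Subtracting the fixed home dose returns the first row of the table, about 85% with the planned test. Alternatively, write the total as Y = X + h, with h the home dose. Regressing Y on arm and h gives the same arm coefficient and standard error as regressing X on arm and h; only the slope on h changes, by 1. In the simulation, a linear model with home dose as covariate has 78-80% power, close to the 81% of the t-test with no home opioid present.

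**The case against.** The hypothesis in sections 4 and 11 is itself about total opioid, so an all-opioid total is a coherent endpoint; opioid beyond the home regimen is a different estimand. That stands, and it is a reason to keep reporting the total. It does not excuse leaving a known, block-independent source of variation unaddressed.

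Participants are aged 18 to 70, walked unaided and can consent, and nothing in the documents shows that any take maintenance opioids. That also stands: the loss is conditional on prevalence and dose, and small at low doses.

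The normality check would usually send such data to the Wilcoxon test. In the simulated cells at 1 to 2 times the mean, normality is rejected in 87-99% of runs, so the very low t-test figures do not describe the planned analysis. The rank test does not protect the mean and SEM that will be reported.

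A deduction is not clean. Home doses may be held, replaced by inpatient orders or taken only as needed. Section 5 itself mentions "opioid tolerance necessitating increased doses, opioid induced hyperalgesia, and opioid dependence", and extra acute need from tolerance would remain after subtraction. A covariate with a free slope can absorb part of that.

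A reader might also infer four stronger claims, which the documents do not support:

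- **Bias toward one arm.** Allocation is random, and simulated type I error stays near or below 5%.
- **Two or three patients generally overwhelm the comparison.** This is fair only for the mean-based comparison at high home doses, or when such patients cluster by chance in one arm.
- **A covariate cannot help.** Step 7 of the working shows that it can.
- **The antihypertensive wording makes the plan inconsistent.** It defines an adverse event. It shows that a home regimen can be identified, and is no more than an analogy for an efficacy total.

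The appendix cited for morphine equivalents is not in the text available and could bear on the point.

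**Conclusion.** The point holds as a gap in the endpoint definition and analysis plan: continued home opioid counts toward the primary total and nothing accounts for it. The consequence is lost precision and a distorted mean and spread for planning the next trial.

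Under the first set of assumptions the planned analysis loses roughly 10 to 17 points of power (86% to 69-76%) when 2 to 3 patients have home doses of 1 to 2 times the mean total. It loses only 2 to 4 points with two patients at 0.25 to 0.5 times the mean. The SD inflation ranges from 1.02- to 1.28-fold at 6% prevalence. All of these inputs are assumed. This is a low-severity improvement, worth making because it is cheap and this is a pilot.

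**What to change.** 1. Record each patient's documented pre-injury opioid or opioid-agonist dose, in morphine equivalents, from the medication list already reviewed at screening.
2. Have blinded staff flag in-hospital doses that are scheduled continuation of that regimen.
3. Before unblinding, state a counting rule for home doses that are held, replaced by another drug or taken as needed.
4. Prespecify one route for the primary comparison: opioid given beyond the scheduled home regimen, analyzed with the planned test; or the total, analyzed in a linear model with home dose as a baseline covariate. The Wilcoxon branch takes no covariate, so the second route replaces the gated choice of test.
5. Report the all-opioid total alongside, with the number of patients on a home regimen in each arm.

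The cost is a few lines of protocol text, a baseline field and a flag on administered doses. The downside is reliance on the accuracy of the home-medication list and on the counting rule; the all-opioid total shows how much the result depends on them. None of this changes how patients are treated.

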The duration of standard local anesthetic formulations vary from 4-8 hours and administration can include single injections or continuous infusion catheters. Liposomal bupivacaine, Exparel®, has a prolonged duration of action of up to 96 hours. Studies have verified its safety with a very low risk of dysrhythmias, local tissue reaction, effects on wound healing or nerve toxicity. In the elective surgical setting, liposomal bupivacaine has been shown to have an opioid sparing effect, increased duration of analgesia, increased patient satisfaction, earlier discharge, and lower hospital cost. This formulation has not been studied in trauma patients and its novel use may impact practice in pain management of trauma patients. Patients may exhibit a lower opioid requirement with the use of the liposomal bupivacaine. In addition, this may reduce the incidence of untoward effects including respiratory depression, central nervous system depression, and gastrointestinal dysfunction, and subsequently speed recovery with improved mobilization and cooperation with physical therapy. To date, no studies have evaluated liposomal bupivacaine regional analgesia following extremity trauma. This pilot study aims to assess the

efficacy of long-acting liposomal bupivacaine compared to ropivacaine 0.2% in orthopedic trauma patients with acute pain following femur or hip fracture.

6) Inclusion and Exclusion Criteria

Inclusion criteria:

- 1) age \geq 18 years \leq 70 years
- 2) Patient's s/p trauma, with confirmed femur and/or hip fractures with a planned admission to the hospital.
- 3) Patient is ambulatory without assistance (e.g. walker, cane, caretaker) prior to incident.

Exclusion Criteria:

- 1) >10 hours since presentation to the emergency department
- 2) History of seizure disorder, recent seizure or a document intra-cranial hemorrhage.
- 3) Central or peripheral neurologic deficit on presentation
- 4) Concern or compartment syndrome
- 5) Associated additional long bone fractures
- 6) End stage liver failure
- 7) Renal failure requiring dialysis
- 8) Pregnancy or breast feeding
- 9) Prisoners
- 10) Coagulopathy with INR >1.5
- 11) Use of direct thrombin inhibitors (bivalirudin, argatroban, desirudin, dabigatran etexilate), or direct factor Xa inhibitors (rivaroxaban, apixaban, edoxaban)
- 12) Suspected prolonged intubation within first 12 hours secondary to respiratory failure other than peri-procedurally
- 13) Adults unable to consent

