Probable/ Likely	
• Event or laboratory test abnormality, with reasonable time relationship to drug intake• Unlikely to be attributed to disease or other drugs• Response to withdrawal clinically reasonable• Rechallenge not required
Possible	
• Event or laboratory test abnormality, with reasonable time relationship to drug intake• Could also be explained by disease or other drugs• Information on drug withdrawal may be lacking or unclear

Unlikely	
 Event or laboratory test abnormality, with a time to drug intake that makes a relationship improbable (but not impossible) Disease or other drugs provide plausible explanations
Conditional/ Unclassified	
 Event or laboratory test abnormality More data for proper assessment needed, or Additional data under examination
Unassessable/ Unclassifiable	
 Report suggesting an adverse reaction Cannot be judged because information is insufficient or contradictory Data cannot be supplemented or verified

The severity of the any potential reaction will be grade using the FDA's guidance for industry. They have been modified to meet the study characteristics and are listed below.

ADVERSE EVENT SEVERITY DEFINITIONS

Vital Signs *	Mild (Grade 1)	Moderate(Grade 2)	Severe (Grade 3)	Potentially Life Threatening (Grade 4)
Dysrhythmia	Unsustained sinus or atrial rhythm < 10 seconds	Unsustained ventricular rhythm <10 secs in duration or sustained sinus rhythms that are asymptomatic	Any rhythm requiring treatment or a change in patient level of care	A ventricular rhythm >10 secs, requiring CPR, cardiac arrest, or any rhythm requiring continuous intravenous therapy
Fever (°C) ** (°F) **	38.0 – 38.4 100.4 – 101.1	38.5 – 38.9 101.2 – 102.0	39.0 – 40 102.1 – 104	> 40 > 104
Tachycardia - beats per minute	101 – 115	116 – 130	> 130	ER visit or hospitalization for arrhythmia
Bradycardia - beats per minute***	50 – 54	45 – 49	< 45	ER visit or hospitalization for arrhythmia
Hypertension (systolic) - mm Hg	141 – 150	151 – 155	> 155	ER visit or hospitalization for malignant hypertension
Hypertension (diastolic) - mm Hg	91 – 95	96 – 100	> 100	ER visit or hospitalization for malignant hypertension
Hypotension (systolic) – mm Hg	85 – 89	80 – 84	< 80	ER visit or hospitalization for hypotensive shock
Respiratory Rate – breaths per minute	17 – 20	21 – 25	> 25	Intubation

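### The mandatory stopping rule rests on severity grades still worded for outpatients, and only unanticipated Grade 3–4 events are routed to the independent monitor

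*Combined protocol and SAP*

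**What the plan says.** The rule is in Section 12, at the end of the outcome definitions: "The study will be stopped if ≥2 patients receiving the active study drug develop the same Grade 3 adverse reaction", or "if one patient develops a Grade 4 or higher adverse reaction". It is worded as mandatory, with no review step.

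The grades are in the two severity tables of Section 15, adapted from FDA guidance. The protocol says of them: "They have been modified to meet the study characteristics and are listed below". Subjects must have "confirmed femur and/or hip fractures with a planned admission to the hospital", and the block is given in the emergency department. A typical Grade 4 entry, for both tachycardia and bradycardia, is "ER visit or hospitalization for arrhythmia".

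On pressure, the only entry limits are in the exclusion "Patients exhibiting signs of shock upon admission, HR >120 or SBP <100 mmHg". Section 12 separately lists as an adverse effect "hypertension requiring antihypertensive pharmacotherapy in addition to the patients home regimen".

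On oversight, Section 15 appoints an independent medical monitor, who also acts as data safety monitor. Grade 3 or 4 events are to be reported to the monitor if they are unanticipated, a term that is not defined. The PI or co-PI is told directly of any severe event, and the PI follows subjects with Grade 3–4 events through their hospitalization.

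**The concern.** A mandatory rule is only as good as the definitions that trigger it. If a grade is defined by a visit or admission that has already happened for another reason, staff must either ignore the definition or guess what it was meant to say. The rule can then fail in two directions. A life-threatening reaction in an inpatient may not count as Grade 4, so the one-patient stop is missed. Conversely, an isolated raised pressure in each of two liposomal bupivacaine patients could be put forward as grounds for ending a 34-patient pilot.

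The reporting route adds to this. The person appointed to give an independent view need not be told of every event that the rule counts.

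**Working it through.** The protocol states no operating characteristics for the rule, so there is no figure to reproduce. The check is a count of the table rows, followed by tracing cases through the text.

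**1. Rows.** Vital signs: dysrhythmia, fever, tachycardia, bradycardia, systolic hypertension, diastolic hypertension, hypotension, respiratory rate = 8. Systemic: nausea/vomiting, dizziness, diarrhea, constipation, headache, fatigue, myalgia, methemoglobinemia = 8. Total 8 + 8 = 16.

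**2. Grade 4 rows that use an emergency visit or hospitalization.**
- With a condition named: tachycardia, bradycardia, systolic hypertension, diastolic hypertension, hypotension, nausea/vomiting, constipation = 7.
- With no condition named: diarrhea, headache, fatigue, myalgia = 4.
- Total 7 + 4 = 11 of 16 (69%).

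The other 16 − 11 = 5 rows (dysrhythmia, fever, respiratory rate, dizziness, methemoglobinemia) do not use this wording. Constipation, counted among the 11, also names disimpaction and perforation, which can be applied to an inpatient.

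**3. Grade 3 rows that use outpatient intravenous treatment.** Nausea/vomiting, dizziness, diarrhea = 3 of 16 (19%). The diarrhea row also has a stool count and a stool weight, so it remains usable.

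**4. A hypotension case.** Suppose a patient on liposomal bupivacaine becomes hypotensive after the block, has no arrhythmia, does not respond to fluid and is given a vasopressor.

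| Place | What follows |
|---|---|
| Section 16b | Counts as local anesthetic toxicity; the blind is broken |
| Section 17, pharmacologic risk | 20% lipid emulsion is given |
| Section 15 table, Grade 3 | Met if systolic pressure is below 80 mm Hg |
| Section 15 table, Grade 4 | Needs an emergency visit or admission for hypotensive shock; the patient is already in hospital for the fracture |
| Stopping rule, Grade 4 limb (one patient) | Not clearly met |
| Stopping rule, Grade 3 limb | Needs a second liposomal bupivacaine patient with the same reaction |

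Below Grade 4, the hypotension row has no treatment term. If the lowest recorded systolic pressure were 80–84 mm Hg, the number alone would read as Grade 2, with or without a vasopressor.

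**5. A hypertension case.** Grade 3 is a systolic pressure above 155 or a diastolic above 100 mm Hg. The table footnote asks for rest. Nothing asks for a repeat reading, a comparison with the pre-block value or a need for treatment. Eligibility has no upper pressure limit, so a patient can enter already in the Grade 3 range. The Section 12 hypertension outcome, by contrast, requires added drug treatment.

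**6. What is counted and what is reported.** The Grade 3 limb counts any matching Grade 3 reaction on the active drug, and the Grade 4 limb counts any Grade 4 reaction. Neither is limited to unanticipated events; the monitor's route is. Section 17 lists nausea, constipation and vomiting as very common (10% or more) with liposomal bupivacaine, and hypotension as common (2% to under 10%). These could be treated as anticipated. The case in step 4 could therefore fall short of the stop and also not be reported to the monitor.

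**The case against.** The best defense is that the main local anesthetic risks are covered. Dysrhythmia at Grade 4 includes a ventricular rhythm beyond 10 seconds, CPR, cardiac arrest and continuous intravenous therapy for a rhythm. Respiratory rate uses intubation, fever a temperature above 40 °C, and methemoglobinemia a level with severe hypoxia or arrest. Section 16b forces unblinding for serious toxicity, the PI is told at once, and the coordinator looks for events daily. This stands, and it confines the Grade 4 problem mainly to hypotension and the rows that name no condition. However, unblinding and PI notification neither trigger the stop nor bring the event to the independent monitor. The column heading (potentially life threatening) may lead an investigator to assign Grade 4 anyway, but that means overriding the cell.

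On pressure, the rule speaks of reactions that patients develop, and Section 15 supplies WHO-UMC causality categories. Pre-existing or pain-related hypertension is thus not plainly countable. That is fair, but no causality level is tied to the rule, and the Possible category admits events that have other explanations.

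On routing, listing a reaction at any grade does not settle that a Grade 3 or 4 instance is anticipated. That also stands; the term needs either a definition or removal.

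A reader might go further and infer that every admitted patient already meets Grade 4. The text does not support this: seven of the eleven rows name a condition, and the rule requires a reaction to develop. The anchors are hard to apply, not automatically met. A reader might also infer that the trial is likely to be stopped falsely. The protocol gives no background rate for pressure readings, and the Section 17 frequencies are not split by grade, so no such probability can be derived. Finally, the headache row's mention of narcotics and the references to daily activity might look like further triggers. In context they most naturally mean an opioid given for the headache and activity limited by the event, so they are wording clarifications only.

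**Conclusion.** The concern holds in a limited form. The severity table was only partly adapted to inpatients: 11 of 16 Grade 4 rows and 3 of 16 Grade 3 rows keep outpatient wording. The consequence that matters most is that vasopressor-dependent hypotension may not trigger the one-patient stop. The loose Grade 3 hypertension definition is a lesser problem in the opposite direction, softened by the attribution implied in the rule. The mismatch between events counted and events sent to the monitor is a separate gap.

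This rests on reading the table cells literally and on finding no other route to the monitor. Part of the protocol between Section 24 and the consent process was not available, so a further route there cannot be excluded. It would be too strong to say that serious reactions would go unnoticed, or that the rule has no usable Grade 4 anchors. No numerical error is claimed. The point is worth fixing because it concerns safety and costs very little to correct.

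**What to change.** 1. **Reporting (Section 15).** Send every Grade 3–4 event to the medical monitor, anticipated or not, with immediate review of any Grade 4 event.
2. **Severity table.** Replace the emergency-visit and hospitalization anchors with life-threatening inpatient criteria: vasopressor support for hypotension; elsewhere, ICU transfer or an urgent life-saving intervention because of the event. Delete the outpatient intravenous wording. Do not substitute routine intravenous antiemetics or fluids as Grade 3, or a prolonged stay as Grade 4. Otherwise one antiemetic dose in each of two patients, or one delayed discharge, could stop the trial.
3. **Grade 3 hypertension.** Require a rise from the pre-block value, confirmed on a repeat resting reading, to a systolic pressure above 155 or a diastolic above 100 mm Hg; or a need for new antihypertensive treatment.

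The cost is a set of table edits and one changed sentence, with no effect on sample size, endpoints or treatment. The monitor would receive a few more reports, and the rule would be slightly less sensitive to isolated pressure readings. A pre-block pressure raised by pain could hide a modest later rise; the new-treatment criterion partly covers this.
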